## **Outcomes of a Longitudinal Multidisciplinary Program for the Treatment of Chronic Pelvic Pain, Incorporating Online and Mobile Applications to Promote Self Efficacy**

The purpose of the study is to determine the impacts of a structured multidisciplinary longitudinal program for the management of chronic pelvic pain with an emphasis on adjunctive web based and mobile applications on patient satisfaction; secondary objectives are to measure the impacts of the treatment plan on quality-of-life measures and pain.

We hypothesize that those patients randomized to a structured chronic pelvic pain management program will demonstrate improved satisfaction with their care, and improved quality of life measures and pain scores as compared to those who receive standard care.

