### **Background:**

The diagnosis and treatment of conditions leading to chronic pelvic pain (CPP) is challenging for patients and providers alike. CPP is defined as pain perceived to originate from the pelvis, lasting greater than 6 months, often associated with negative cognitive, behavioral, sexual and emotional consequences. While CPP is estimated to affect 26% of the world's female population, and accounts for 10% of gynecologic office visits, there is a lack of high-quality evidence to support the use of many well accepted therapeutic interventions. It has, however, been well established that treatments should be multimodal in order to address the overlapping non-gynecologic pain disorders and biopsychosocial factors impacting many patients with CPP. A growing body of evidence has demonstrated improved pain severity and quality of life measures for patients receiving care in interdisciplinary centers, able to provide coordinated surgical, medical and/or pain management care in a centralized location. Other studies have examined care delivered in tertiary care center clinics, relying on a multidisciplinary approach in which patients received care from a variety of providers both central to the clinic and in their referral networks. Although effective, the aforementioned approach dictates a specialized allocation of resources not widely available for the treatment of CPP in this moment. While the later multidisciplinary model may be more feasible in this current environment, it demands that patients are able to navigate care delivered from a variety of providers. Patients in turn may face financial constraints, time constraints, or a perceived lack of utility of the prescribed treatments leading to poor adherence. With widely available access to smart phones and the internet, we may consider how to incorporate mobile and web-based applications to supplement the multidisciplinary treatment of CPP in a way that alleviates barriers to care. There already exist a variety of resources dedicated to patient education and self-management which have been found to effectively help individuals with chronic pain conditions. Improvements in self efficacy and depression, as well as decreased health service usage have also been established when these apps are supplemented with proactive calls encouraging app compliance. Current practice at our tertiary care center relies upon a multidisciplinary model in which patients' surgical and medical management of chronic

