
pain is performed by clinic providers, and outside referrals are provided for complex pain management, pelvic floor therapy and psychotherapy services. We propose that formalizing the structure of our chronic pelvic pain management through the clear definition of available resources, supplemented with mobile and web-based applications supporting education and self-efficacy with the aim of reducing barriers to care, paired with a well-defined timeline for follow up, we will see improved patient satisfaction, improved quality of life and pain scores as opposed to patients enrolled in standard practice.

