#### Study Intervention:

Patients randomized to the intervention arm will receive standard care in addition to a Chronic Pelvic Pain Handbook which outlines their diagnoses and includes educational materials, an individualized treatment plan and follow up schedule.

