#### Procedures Involved:

Patients meeting eligibility criteria will be approached regarding their interest in participating. Should they choose to participate they will be randomized using a random number generator- an odd number will designate randomization to the control group, while an even number will designate randomization to the intervention group. Those in the control arm will receive standard care which is individualized based on their specific needs and may include medical, procedural or surgical interventions. Those in the intervention arm will receive standard care in addition to our Chronic Pelvic Pain Handbook which includes educational resources pertinent to their specific diagnosis, defines available treatment resources, provides a clearly defined follow up schedule and points of contact. Resources included in the Chronic Pain Handbook were thoroughly reviewed by the study team and providers within the National Center for Advanced Pelvic Surgery team. They were screened to be sure that medically accurate information was being presented and that recommendations reflect best practices for the treatment of chronic pelvic pain based on expert consensus. The diagnoses designated on page 4 of the handbook will be filled out by the provider the patient is seeing in the office. Baseline demographics will be collected in addition to validated surveys measuring quality of life and pain scores for all participants. These surveys will be repeated at 3 months, 6 months and 12 months following initial enrollment. Patients' satisfaction with their treatment will also be measured at 3 months, 6 months and 12 months.

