#### Data Collected:

Baseline demographic and pain related data including age, race/ethnicity, BMI, age when pain started, prior treatments, smoking status, history of anxiety/depression/sexual assault, current or prior engagement in psychotherapy, family history of chronic pain will be collected through chart review and patient interview at time of their scheduled visit.

Measurements of pain and quality of life will be collected through previously validated questionnaires regarding pelvic pain (Yosef et al, 2016), in addition to the PHQ-9, GAD-7, Pain Catastrophizing Scale, and Pain Self Efficacy Questionnaire.

Patient satisfaction data will be collected using the PSQ-18 with additional questions included regarding specific barriers they have experienced, what web based or mobile applications they have used and the degree to which they found them helpful.

The number of visits outside of scheduled follow ups, as well as number of patient portal messages sent between visits will be obtained through chart review.

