#### Recruitment Methods:

Subjects will be screened for eligibility based on chart review conducted prior to their scheduled appointment. If eligible they will be contacted in advance of their appointment to determine their interest in participation. If they are interested in participating, they will be verbally consented and randomized prior to the appointment. This will be performed remotely by the study coordinator. A message will be sent to the provider they are seeing and a note placed in the medical record to designate their participation and treatment arm. The patient will then be seen by their National Center for Advanced Pelvic Surgery provider, whom are listed as sub-investigators on the project.

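### Does the emphasis on web and mobile applications leave the randomized comparison undefined?

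*Protocol*

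**What the plan says.** The purpose statement under the protocol's title describes a "structured multidisciplinary longitudinal program for the management of chronic pelvic pain with an emphasis on adjunctive web based and mobile applications". The hypothesis that follows is simpler: patients randomized to a structured management program will do better on satisfaction, quality of life and pain than patients who receive standard care.

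The Background says "Current practice at our tertiary care center relies upon a multidisciplinary model", with outside referrals for pain management, pelvic floor therapy and psychotherapy. It proposes to formalize that care with clearly defined resources and a timeline for follow-up, "supplemented with mobile and web-based applications supporting education and self-efficacy with the aim of reducing barriers to care".

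The arms are defined in two places. Study Intervention gives the intervention arm "standard care in addition to a Chronic Pelvic Pain Handbook which outlines their diagnoses and includes educational materials", together with an individualized treatment plan and a follow-up schedule. Procedures Involved adds that the Handbook "defines available treatment resources, provides a clearly defined follow up schedule and points of contact". For the comparator it says: "Those in the control arm will receive standard care which is individualized based on their specific needs".

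Under Data Collected, the satisfaction questionnaire carries extra questions, including "what web based or mobile applications they have used and the degree to which they found them helpful". Under Recruitment Methods, the provider is told of the patient's participation and arm by message and chart note, and then: "The patient will then be seen by their National Center for Advanced Pelvic Surgery provider".

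**The concern.** The Background names three things to be added to current practice: defined resources, applications and a follow-up timeline. Two of them can be found again in the arm definitions. The third, which the title and purpose single out, cannot. Neither Study Intervention nor Procedures Involved uses the word, names a product or says how a patient would be given one.

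The control side is also open. Standard care is individualized, no rule says whether applications may be recommended, and no separate set of providers is described for each arm. Providers at the center helped review the Handbook's resources, so a clinician who knows its content may also treat controls. If controls used the same applications, the arms would differ less on the element that the purpose emphasizes.

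Finally, both arms receive care that is already multidisciplinary, so that feature is not what is randomized. A reader who goes by the title could credit a positive result to multidisciplinary care or to applications, and the design isolates neither.

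**Working it through.** The protocol gives no sample size, effect size or usage rate that bears on this point, so there is no figure to reproduce. The check is a comparison of the sections.

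**1. What is claimed against what is randomized.**

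| Element | Purpose or Background | Intervention arm | Control arm |
|---|---|---|---|
| Multidisciplinary care | Named in the purpose; described as current practice | Yes, through standard care | Yes, through standard care |
| Defined treatment resources | Proposed addition | In the Handbook | Not stated |
| Follow-up timeline | Proposed addition | In the Handbook | Not stated |
| Web and mobile applications | Proposed addition, emphasized | Not named; Handbook holds educational material and resources | Not stated |
| Individualized plan, points of contact | – | In the Handbook | Care individualized; no Handbook |

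Row by row, the randomized difference is the Handbook package added to standard care. The observation that the arm definitions do not mention applications is correct.

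**2. Does the hypothesis need more than this?** It sets a structured program against standard care. It does not assert an effect of applications by themselves, or of multidisciplinary care against care that is not multidisciplinary. The Background describes formalizing care that it has just called multidisciplinary, so the incremental nature of the comparison is disclosed. The contrast that is randomized is the contrast that is hypothesized.

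**3. Is the application content really absent?** The Handbook exists as a separate document: Procedures Involved refers to a specific page of it and reports that its resources were reviewed. The Background speaks of existing resources for education and self-management and calls them apps in the next sentence. Procedures Involved then places educational resources in the Handbook. The link is implicit, and the item list would naturally sit in the Handbook. That document is not at hand, so its content can be neither confirmed nor denied.

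**4. Could control use spoil the comparison?** Suppose a share *p* of the intervention arm and *c* of controls use the same applications, and that benefit is proportional to use. The application part of the difference then keeps a fraction (*p* − *c*)/*p* of its value without control use. At *c* = 0 this is 100%, and at *c* = *p* it is 0%. The protocol gives neither *p* nor *c*, so the formula returns the whole range and cannot say whether there is a problem. It also leaves the other parts of the package untouched. Where the comparator is individualized standard care, applications that a provider would suggest anyway are part of that comparator, and the difference between arms is still the effect of adding the Handbook to it.

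**5. Can application use be seen afterwards?** Yes, if the survey is given as described. The application questions accompany the satisfaction questionnaire, which is scheduled at 3, 6 and 12 months, and nothing restricts them to one arm.

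**The case for a change.** The strongest case for a change is that what each arm receives is for the protocol to define. A statistical analysis plan can say how application use is summarized, but it cannot settle what was delivered. The element stressed in the title deserves a stated content, and one sentence would supply it at almost no cost. Even if the Handbook lists every application, the protocol would still be silent on controls.

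Part of this stands. The arm definitions could be more explicit, and a sentence saying that the Handbook's resources include applications, and whether standard care may include them, would help a reader. But that sentence would describe the trial more fully without altering it. The intervention is fixed by reference to an existing, reviewed document, and the comparator is fixed as whatever standard care contains. Providers are told each patient's arm, so a control is not handed the Handbook merely because the provider does not know the allocation. That controls will be given the same applications is a possibility, and nothing in the protocol says that it will happen.

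A narrower title is a matter of preference. The intervention arm does receive a multidisciplinary program with the structured additions, so naming the trial after the whole program is not false.

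**Conclusion.** No change to the plan is needed. The mismatch between an emphasis on applications and arm definitions that do not mention them is real, but it is a gap in description. The comparison of the Handbook package plus standard care with standard care alone is valid, matches the hypothesis, and is the same whether or not the applications are listed in the protocol. Randomization, the primary satisfaction endpoint and the analysis of the difference between arms are unaffected.

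No numerical size can be attached: any dilution depends on application use in each arm, for which the protocol gives no figures.

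The conclusion rests on two assumptions. The first is that the Handbook, which was not available here, carries the application content that the Background describes. If it does not, the package comparison still stands, but the title would promise something that was not delivered. The second is that the results are read as the effect of the whole package. A competent report would do this from the design alone, and would not attribute a difference to applications or to multidisciplinary care separately.

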### **Background:**

The diagnosis and treatment of conditions leading to chronic pelvic pain (CPP) is challenging for patients and providers alike. CPP is defined as pain perceived to originate from the pelvis, lasting greater than 6 months, often associated with negative cognitive, behavioral, sexual and emotional consequences. While CPP is estimated to affect 26% of the world's female population, and accounts for 10% of gynecologic office visits, there is a lack of high-quality evidence to support the use of many well accepted therapeutic interventions. It has, however, been well established that treatments should be multimodal in order to address the overlapping non-gynecologic pain disorders and biopsychosocial factors impacting many patients with CPP. A growing body of evidence has demonstrated improved pain severity and quality of life measures for patients receiving care in interdisciplinary centers, able to provide coordinated surgical, medical and/or pain management care in a centralized location. Other studies have examined care delivered in tertiary care center clinics, relying on a multidisciplinary approach in which patients received care from a variety of providers both central to the clinic and in their referral networks. Although effective, the aforementioned approach dictates a specialized allocation of resources not widely available for the treatment of CPP in this moment. While the later multidisciplinary model may be more feasible in this current environment, it demands that patients are able to navigate care delivered from a variety of providers. Patients in turn may face financial constraints, time constraints, or a perceived lack of utility of the prescribed treatments leading to poor adherence. With widely available access to smart phones and the internet, we may consider how to incorporate mobile and web-based applications to supplement the multidisciplinary treatment of CPP in a way that alleviates barriers to care. There already exist a variety of resources dedicated to patient education and self-management which have been found to effectively help individuals with chronic pain conditions. Improvements in self efficacy and depression, as well as decreased health service usage have also been established when these apps are supplemented with proactive calls encouraging app compliance. Current practice at our tertiary care center relies upon a multidisciplinary model in which patients' surgical and medical management of chronic

pain is performed by clinic providers, and outside referrals are provided for complex pain management, pelvic floor therapy and psychotherapy services. We propose that formalizing the structure of our chronic pelvic pain management through the clear definition of available resources, supplemented with mobile and web-based applications supporting education and self-efficacy with the aim of reducing barriers to care, paired with a well-defined timeline for follow up, we will see improved patient satisfaction, improved quality of life and pain scores as opposed to patients enrolled in standard practice.

#### Study Endpoints:

The primary endpoint will be patient satisfaction scores related to their treatment for chronic pelvic pain. Secondary endpoints will be quality of life and pain scores.

#### Study Intervention:

Patients randomized to the intervention arm will receive standard care in addition to a Chronic Pelvic Pain Handbook which outlines their diagnoses and includes educational materials, an individualized treatment plan and follow up schedule.

#### Procedures Involved:

Patients meeting eligibility criteria will be approached regarding their interest in participating. Should they choose to participate they will be randomized using a random number generator- an odd number will designate randomization to the control group, while an even number will designate randomization to the intervention group. Those in the control arm will receive standard care which is individualized based on their specific needs and may include medical, procedural or surgical interventions. Those in the intervention arm will receive standard care in addition to our Chronic Pelvic Pain Handbook which includes educational resources pertinent to their specific diagnosis, defines available treatment resources, provides a clearly defined follow up schedule and points of contact. Resources included in the Chronic Pain Handbook were thoroughly reviewed by the study team and providers within the National Center for Advanced Pelvic Surgery team. They were screened to be sure that medically accurate information was being presented and that recommendations reflect best practices for the treatment of chronic pelvic pain based on expert consensus. The diagnoses designated on page 4 of the handbook will be filled out by the provider the patient is seeing in the office. Baseline demographics will be collected in addition to validated surveys measuring quality of life and pain scores for all participants. These surveys will be repeated at 3 months, 6 months and 12 months following initial enrollment. Patients' satisfaction with their treatment will also be measured at 3 months, 6 months and 12 months.

#### Data Collected:

Baseline demographic and pain related data including age, race/ethnicity, BMI, age when pain started, prior treatments, smoking status, history of anxiety/depression/sexual assault, current or prior engagement in psychotherapy, family history of chronic pain will be collected through chart review and patient interview at time of their scheduled visit.

Measurements of pain and quality of life will be collected through previously validated questionnaires regarding pelvic pain (Yosef et al, 2016), in addition to the PHQ-9, GAD-7, Pain Catastrophizing Scale, and Pain Self Efficacy Questionnaire.

Patient satisfaction data will be collected using the PSQ-18 with additional questions included regarding specific barriers they have experienced, what web based or mobile applications they have used and the degree to which they found them helpful.

The number of visits outside of scheduled follow ups, as well as number of patient portal messages sent between visits will be obtained through chart review.

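### Does the lack of any planned record of treatments and referrals after enrolment undermine the comparison of satisfaction between arms?

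*Protocol*

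**What the plan says.** The Protocol's Study Endpoints section states: "The primary endpoint will be patient satisfaction scores related to their treatment for chronic pelvic pain". Quality of life and pain are secondary. Under Procedures Involved, satisfaction is measured at 3, 6 and 12 months, and the quality-of-life and pain surveys are taken at baseline and at the same three times.

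Both arms receive standard care. Procedures Involved describes it, for the control arm, as "standard care which is individualized based on their specific needs and may include medical, procedural or surgical interventions". The Background adds that in current practice "outside referrals are provided for complex pain management, pelvic floor therapy and psychotherapy services". The intervention arm also receives a handbook that, according to Study Intervention, contains educational material and "an individualized treatment plan and follow up schedule". Recruitment Methods has the treating provider, a sub-investigator, told of the patient's participation and arm by message and by a note in the record.

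Data Collected lists four groups of items:

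- baseline data, among them prior treatments and "current or prior engagement in psychotherapy";
- questionnaires on pain, mood, catastrophizing and self-efficacy;
- the PSQ-18, with added questions on barriers met, applications used and their helpfulness;
- from chart review, "The number of visits outside of scheduled follow ups, as well as number of patient portal messages sent between visits".

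No section lists treatments, procedures, surgery or referrals after enrolment as data.

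**The concern.** Patients are asked to rate their treatment, but what that treatment consisted of is not on the list of data. It cannot be inferred from the arm, because standard care is individualized in both. The provider usually knows the arm before the first study visit and might treat or refer differently for reasons unrelated to the handbook.

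The Protocol's rationale also runs partly through the uptake of care. The Background says patients may face "financial constraints, time constraints, or a perceived lack of utility of the prescribed treatments leading to poor adherence", and it proposes a formal structure "with the aim of reducing barriers to care, paired with a well-defined timeline for follow up". A reader would naturally want to know whether patients in the intervention arm then received more, or different, care.

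The stake is interpretation. If satisfaction differed, one could not fully tell whether patients were rating the handbook, the care it led to, or a change in provider behaviour. If satisfaction did not differ, one could not fully tell whether care had changed at all. A missing data item is also a protocol matter: no analysis plan can supply it afterwards.

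**Working it through.** The Protocol gives no figure on this point, so the check is a reading of its sections against one another.

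**1. Is the omission real?** Yes. Prior treatments and psychotherapy engagement belong to the baseline list. After enrolment, the items that bear on care are unscheduled visits, portal messages, barriers, and applications with their helpfulness. None records what treatment was given. The items of the cited pelvic-pain questionnaire cannot be seen, but the Protocol presents it as a measure of pain and quality of life.

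**2. Does any endpoint depend on the missing items?** No. Satisfaction comes from the PSQ-18, and quality of life and pain come from the repeated questionnaires. All can be scored and compared without knowing which treatments were given.

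**3. Does the comparison between arms depend on them?** No. The contrast is standard care against standard care plus handbook. The handbook carries a treatment plan, a list of resources and a follow-up schedule, so some change in care is an intended consequence of assignment. A comparison of patients as randomized includes that change. Providers' awareness of the arm is largely unavoidable with this intervention, since the provider fills in the diagnoses in the handbook.

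**4. Could the items improve the analysis if collected?** They arise after randomisation and lie partly on the path by which the handbook may act. Adjusting the primary comparison for them would remove part of the effect of interest and could introduce bias. Only a description by arm remains, and it would not show whether a difference in care came from the handbook or from the provider's knowledge of the arm.

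**5. Is the intended mechanism left unmeasured?** Only in part. The title and Background emphasise self-efficacy, education, fewer barriers and a defined timeline. Data Collected includes the Pain Self Efficacy Questionnaire, questions on barriers and on applications, and the count of unscheduled visits. Uptake of treatments and referrals is a reasonable further link, but it is inferred from the rationale and is not stated as an objective.

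**6. Are the data lost if the list stays as it is?** Mostly not. The Background says clinic providers carry out surgical and medical management, and chart review is already planned, so care charted at the centre could probably be abstracted later. The part at risk is the uptake of outside referrals. Adding fields to the chart review would capture that part poorly. Capture might also differ by arm: only the intervention arm is described as having a clearly defined follow-up schedule and points of contact, and more contact with the centre could mean fuller charting of outside care. Using the same abstraction method in both arms would not remove that imbalance.

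**The case for a change.** The best argument for a change is that a trial whose primary outcome is satisfaction with treatment ought to record the treatment. The listed counts measure contacts, not care. The count of visits outside scheduled follow-up also depends on the schedule, which is described as clearly defined for the intervention arm only. Chart review is already planned, so extra fields would cost little and are best specified at the outset. A description of care by arm would help a reader judge how the result arose and how far it might carry to other clinics.

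Most of this stands as a statement of what would be informative. The omission is real, and fields specified in advance are better than later abstraction. It does not show that the plan is wrong. The Protocol makes no false statement here and promises no data on care received. The argument identifies no bias in the comparison of arms as assigned. The ambiguity that motivates it, handbook or provider behaviour, would remain after the fields were added. The hardest item to recover later, outside care, is also the one that chart review would measure least well.

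**Conclusion.** No change to the plan is needed. Care received after enrolment would be visible only in part, but the randomized comparison of satisfaction, quality of life and pain stands without it, and the extra items would alter no planned result. The size and direction of any difference in care between arms cannot be derived from the Protocol.

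This rests on three assumptions: that the question is the effect of offering the handbook on top of standard care, as the Protocol describes it; that patients are compared in the arms to which they were randomized; and that care given at the centre remains in records open to later review. If the sponsor wanted to claim that the handbook acts by increasing the uptake of particular treatments, the listed data would not support that claim, but the Protocol sets no such objective. Describing treatments and referrals by arm would be a sensible option, provided readers are told that outside care may be captured incompletely and unequally.
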